2.1.1 Rationale for Ensemble Confidence Assessment

Our decision to utilize ensemble-based confidence signals rather than single-model self-assessment is grounded in extensive empirical evidence of LLM calibration failures. LLMs frequently exhibit overconfidence, expressing high certainty even when producing factually incorrect outputs [1]. Recent studies confirm these challenges persist in state-of-the-art models; standard prompting often yields poorly calibrated estimates that self-reflection mechanisms alone cannot rectify, particularly in high-stakes medical and scientific domains [2, 3].

To address this, we estimate confidence via an ensemble of three distinct LLMs, and use the mean score as a selective-attention cue. This shifts confidence estimation away from unreliable internal self-reports toward practical uncertainty quantification. By aggregating judgments from multiple models, we reduce sensitivity to any single model’s miscalibration. When independently queried models disagree, the case may be genuinely ambiguous, warranting heightened human review. In the clinical context, this approach offers two critical advantages. First, the mean confidence score serves as a “soft cue” to modulate physician attention. Second, the architecture remains scalable; modern API frameworks allow for parallel querying with minimal latency overhead [4]. Ultimately, we treat the ensemble mean not as a definitive probability, but as a robust heuristic to safeguard against overstated confidence typical of single-model architectures.

2.2 Participants

2.2.1 Inclusion Criteria

- Full or Provisionally Registered Medical Practitioners with the Pakistan Medical and Dental Council (PMDC).
- Completed Bachelor of Medicine, Bachelor of Surgery (MBBS) Exam. The equivalent degree of MBBS in the US and Canada is the Doctor of Medicine (MD).
- Participants must have completed a structured training program on the use of ChatGPT-4o (or a comparable large language model), totaling at least 10 hours of instruction. The program must include hands-on practice related to the LLM's key aspects, specifically prompt engineering and content evaluation.

2.2.2 Exclusion Criteria

- Any other Registered Medical Practitioners (Full or Provisional) with PMDC (e.g., professionals with Bachelor of Dental Surgery or BDS).

2.3 Sample Size and Power Analysis

Target Sample Size: 50 participants (25 per arm).

Power Calculation: Based on pilot data and similar studies, we assume:

- An effect size (difference in mean diagnostic reasoning scores) of 8 percentage points between groups.
- A standard deviation of 16.2%.
- An intraclass correlation coefficient (ICC) between 0.05 and 0.15 (to account for clustering of cases within participants).
- An average of 4 completed cases per participant.

With these assumptions, a sample size of 50 provides $\geq 80\%$ power to detect a significant difference in the primary outcome, diagnostic reasoning score, between the two groups using a linear mixed-effects model ($\alpha = 0.05$, two-sided).

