Mitigating Automation Bias in Physician-LLM Diagnostic Reasoning Using Behavioral Nudges

[name], [name], [name],
[name], [name]

Study Protocol and Statistical Analysis Plan

Document Date: December 26, 2025

1 Introduction

Automation bias presents substantial risks in clinical environments, particularly as artificial intelligence (AI) tools become more integrated into healthcare workflows. This cognitive phenomenon describes the tendency of individuals to favor suggestions from automated decision-making systems, even when those suggestions are incorrect. While Large Language Models (LLMs), such as ChatGPT-5.1, hold promise for reducing diagnostic errors by augmenting clinical reasoning, concerns arise about their potential to amplify cognitive biases. Of particular concern is the propensity of LLMs to *hallucinate*, generating plausible but false information, which, when combined with automation bias, can lead clinicians to accept erroneous recommendations without adequate scrutiny.

The emergence of automation bias in medical contexts reflects a complex interplay of environmental and psychological factors. Time constraints in high-volume clinical settings create pressure to accept AI-generated recommendations without adequate scrutiny. Financial incentives that prioritize efficiency over thoroughness may further discourage the critical evaluation necessary for sound clinical judgment. Cognitive fatigue during extended shifts diminishes physicians' capacity for sustained analytical thinking. These contextual pressures interact with psychological mechanisms including diffusion of responsibility, overconfidence in technological solutions, and cognitive offloading, collectively creating conditions where uncritical acceptance of AI-generated recommendations becomes more likely.

This randomized controlled trial evaluates the effectiveness of a behavioral nudge intervention designed to mitigate automation bias among medical doctors utilizing LLM-generated diagnostic recommendations. The primary objective is to determine whether this intervention improves diagnostic reasoning performance scores when physicians evaluate clinical vignettes that include deliberately flawed LLM recommendations. Secondary objectives include assessing whether physician experience level, gender, and prior LLM experience moderate the intervention's effectiveness.

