1.2 Hypotheses

- **Primary Hypothesis (H1):** Physicians receiving the behavioral nudge intervention (baseline accuracy information and case-specific color-coded confidence signals) will demonstrate significantly higher diagnostic reasoning scores when evaluating clinical vignettes with deliberately flawed LLM recommendations compared to physicians receiving the same LLM recommendations without the nudge.
- **Secondary Hypotheses:**
 - **H2:** Physicians with less clinical experience will exhibit greater baseline automation bias and show larger treatment effects from the nudge intervention compared to more experienced clinicians.
 - **H3:** The intervention will demonstrate greater effectiveness for red-signal (below-baseline) versus orange-signal (above-baseline) recommendations.

2 Methods

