2.1 Study Design

This study will be a single-blind, randomized controlled trial with two parallel arms. Participants will be randomly assigned in a 1:1 ratio to the intervention arm or to the control arm. To control for variability in user prompting skills, participants will not interact directly with a live LLM chat interface. Instead, they will use a custom-built web platform that displays the clinical vignette and provides access to pre-generated LLM recommendations.

- **Control Arm:** Participants will evaluate six clinical vignettes (three with deliberately flawed diagnostic information and three with correct information). Through the study platform, they will be able to view “LLM Diagnostic Recommendations” generated by ChatGPT. These recommendations will be presented in a standard, neutral text format without additional context or nudge.
- **Intervention Arm:** Participants will evaluate the same six clinical vignettes using the same web platform, but with a behavioral nudge embedded directly within the LLM suggestion interface. Upon expanding the LLM recommendation panel for any vignette, participants will be presented with two synchronized cognitive cues:

1. **Anchoring Cue:** Displayed at the top of the panel, this visual cue presents ChatGPT’s baseline diagnostic accuracy on standard medical datasets (e.g., Medbullets). This serves to explicitly anchor expectations to the model’s realistic performance level, preventing both excessive skepticism and uncritical acceptance, before the participant reads the specific recommendation.
2. **Selective Attention Cue:** Below the baseline accuracy information, each case-specific LLM recommendation will be displayed alongside a color-coded signal reflecting the ensemble confidence for that particular recommendation. This score is derived from a consensus evaluation by three independent state-of-the-art LLMs (e.g., Claude 4.5 Sonnet, Gemini 2.5 Pro Thinking, and GPT-5.1) to mitigate single-model miscalibration:
 - **Red Signal:** Displayed when the ensemble’s mean confidence falls below ChatGPT’s established baseline accuracy, signaling a high-uncertainty case that requires deeper critical evaluation and indicating “*The LLM is less sure about this case than it usually is*”.

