2.4 Clinical Vignettes & LLM Recommendations

Participants will evaluate six clinical vignettes specifically designed to measure automation bias. These vignettes will:

- Be based on modified real cases.
- Represent a range of diagnostic complexity across common medical specialties.
- Avoid overly simplistic or extremely rare conditions.
- Follow a standardized format, including:
 - Chief complaint and history of present illness.
 - Relevant past medical, social, and family history.
 - Physical examination findings.
 - Initial laboratory results.
- Include three clinical vignettes whose LLM recommendations contain deliberately introduced clinical reasoning errors and three with accurate recommendations, presented in randomized order. A panel of three licensed physicians will design these errors to be subtle yet clinically significant and detectable by trained clinicians.

- For every vignette, the LLM's recommendations will be pre-generated and fixed. This ensures all participants see identical recommendations for each vignette, the same error in flawed cases and the same correct reasoning in accurate cases, eliminating variance from real-time model variability.

Vignette Selection and Validation:

- A pool of 10 potential vignettes will be created and reviewed by an independent panel of three experienced medical doctors for:
 - Clinical accuracy and realism.
 - Appropriateness of difficulty level.
 - Clarity and completeness of information.
 - In flawed vignettes: subtlety and clinical significance of the introduced errors (errors should be detectable by competent physicians but not immediately obvious).
- Six vignettes will be selected based on the panel's ratings and feedback, aiming for a balanced representation of medical specialties and diagnostic challenges.
- For intervention arm participants, LLM output will be pre-generated and standardized for each vignette to ensure consistency in the presentation of correct or flawed information.

Vignette Completion:

- Each participant will complete all six vignettes in a single, proctored, approximately 75-minute session.
- The order of vignettes will be randomized for each participant to control for order effects and prevent pattern recognition.

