4.2 Primary Outcome Analysis

- A linear mixed-effects model will be used to compare the mean diagnostic reasoning accuracy score between the intervention and control groups.
- **Model Structure:**
 - **Dependent Variable:** Diagnostic reasoning performance score (percentage).
 - **Fixed Effect:** Treatment group (Intervention vs. Control).
 - **Random Effects:**
 - * Participant ID (to account for within-participant correlation across cases).
 - * Vignette ID (to account for potential variability in case difficulty).
 - **Covariates:**
 - * Years of practice post MBBS, gender, and prior experience with LLMs.
- **Primary Comparison:** The difference in mean diagnostic reasoning scores between the two groups, adjusted for random effects and covariates.
- **Significance Threshold:** A two-sided p-value ≤ 0.05 will be considered statistically significant.

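### Section 2.3 powers the trial on 4 vignettes per participant although Section 2.4 has six; H1 concerns only the three flawed ones while the Section 4.2 model pools all six, so the stated power is tied to no single vignette set

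*Combined protocol and SAP*

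**What the plan says.** **Number of vignettes.** Section 2.3 assumes 25 participants per arm, a difference of 8 percentage points, an SD of 16.2%, and an ICC of 0.05 to 0.15 "to account for clustering of cases within participants". Its last input is "An average of 4 completed cases per participant". From these it claims at least 80% "power to detect a significant difference in the primary outcome, diagnostic reasoning score, between the two groups using a linear mixed-effects model", at a two-sided 0.05 level. Section 2.4, under Vignette Completion, says: "Each participant will complete all six vignettes in a single, proctored, approximately 75-minute session". Nothing in the document explains the 4.

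**Which vignettes.** H1 in Section 1.2 predicts "significantly higher diagnostic reasoning scores when evaluating clinical vignettes with deliberately flawed LLM recommendations". The primary objective in the Introduction asks whether the nudge "improves diagnostic reasoning performance scores when physicians evaluate clinical vignettes that include deliberately flawed LLM recommendations". Section 2.1 describes the six as "three with deliberately flawed diagnostic information and three with correct information". The Section 4.2 model has treatment group as its fixed effect, random effects for participant and vignette, and three participant-level covariates. It is not restricted to flawed vignettes and has no term separating flawed from accurate ones. The paragraph in Section 2.1 on measuring change in automation bias likewise defines the primary measure as the difference in mean scores between arms, without naming a subset.

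**The concern.** There are two mismatches, and they should be kept apart.

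The first is a sizing input that disagrees with the session design: 4 vignettes in the power statement, six in the session.

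The second matters more. The primary hypothesis is about three vignettes and the primary model is about six. The 4 belongs to neither, and it cannot describe a test of H1 as worded, because only three flawed vignettes exist. Section 2.3 also leaves open whether the 8 points is a difference over all six or over the flawed three. A nudge against uncritical acceptance of wrong advice has its most obvious target in the flawed vignettes. If little happens in the accurate ones, pooling dilutes the effect.

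Two things are at stake. A null result could not be read as planned if the power figure belongs to a different set of vignettes from the test. And while the set is open, the choice between a flawed-only and a pooled test could be made after the results are known.

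**Working it through.** **Inputs.** From Section 2.3: n = 25 per arm, SD 16.2, difference 8, ICC 0.05 to 0.15, two-sided 0.05. The number of vignettes m is 4 (Section 2.3), 6 (Section 2.4), or 3 (H1 with Section 2.1). Section 2.3 does not state the level of the SD; it is read here as the total SD of one vignette score. The same SD and ICC are assumed for the flawed subset, and covariates are ignored.

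**Formulas.** SD of a participant's mean = 16.2 × √(ICC + (1 − ICC)/m). Standard error of the arm difference = that SD × √(2/25). Power comes from the noncentral t with 48 degrees of freedom and noncentrality = difference / standard error.

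**The plan's own figure (m = 4, ICC 0.15).** 16.2 × √(0.15 + 0.85/4) = 9.75. Standard error 9.75 × 0.2828 = 2.76. Noncentrality 8/2.76 = 2.90. Power 81.1%. At ICC 0.05 it is 89.1%. The claim of at least 80% is reproduced over the whole ICC range.

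**Check on the SD reading.** Taken as the SD of participant means, 16.2 gives only 40-42% power. Taken as a residual SD, it gives 75-76% at m = 4 and ICC 0.15. Neither reproduces the claim across the range, so the vignette-level total SD is kept.

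**The same calculation for each set:**

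| Set and difference | ICC 0.05 | ICC 0.10 | ICC 0.15 |
|---|---|---|---|
| 4 vignettes, 8 points | 89.1% | 85.1% | 81.1% |
| Six pooled, 8 points | 96.3% | 92.8% | 88.6% |
| Three flawed, 8 points | 80.7% | 77.2% | 73.9% |
| Six pooled, 4 points | 46.6% | 40.2% | 35.4% |

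For three vignettes at ICC 0.15: 16.2 × √(0.15 + 0.85/3) = 10.66, standard error 3.02, noncentrality 2.65. Power falls below 80% once the ICC passes about 0.06 (about 0.08 by the normal approximation, which gives 76-82% over the range).

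**Where the 4 points come from.** If the effect is 8 on the three flawed vignettes and e on the three accurate ones, the pooled effect is (3 × 8 + 3 × e)/6 = 4 + e/2. The documents do not give e. For e from 0 to 8 the pooled effect runs from 4 to 8 points, and power with six vignettes from 35-47% up to 89-96%.

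**Allowing for the vignette random effect.** Every participant sees the same vignettes, so with full completion the variance between vignettes cancels from the arm comparison. If vignettes carry a share v of the total variance, the SD of a participant's mean becomes 16.2 × √(ICC + (1 − ICC − v)/m). With an assumed v of 0.20 and m = 3, power is 87.8%, 84.2% and 80.7% at the three ICCs. For the 4-point pooled effect the same share gives 53.4%, 45.2% and 39.1%.

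**The case against.** The strongest reply is that no stated figure is wrong. Section 2.3 claims power for the mixed model on the primary outcome. With its own inputs the claim holds at every stated ICC, and using 4 where six are assigned is conservative. The 74-81% belongs to a flawed-only test that neither Section 4.2 nor the definition of the primary measure in Section 2.1 specifies. That shortfall is also small, and vignette variance absorbed by the model could remove it.

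Most of this stands. The 4 against six mismatch alone does not weaken a pooled test, provided that 8 points is the pooled effect. The flawed-only shortfall is at most about 6 points and depends on an unknown vignette share. The reply does not, however, reconcile the hypothesis with the model, and Section 2.3 does not say that the 8 points is pooled. The reassurance rests on exactly what is left unstated.

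Three stronger readings are tempting, and the documents do not support them.

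- A reader might infer that the trial is underpowered. That depends on which vignettes the 8 points describe. If 8 were a pooled effect arising only in flawed vignettes, the flawed-only effect would be 16 points and power for H1 would exceed 99%.
- A reader might infer that a third of the vignettes are expected to be missing (2 of 6). Section 2.3 never calls the 4 an allowance for non-completion.
- A reader might infer that more participants are needed. Nothing here establishes that.

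**Conclusion.** The point holds as an inconsistency that should be corrected, not as proof of inadequate power. The sizing input of 4 contradicts the six-vignette session, and the primary hypothesis and primary model cover different sets of vignettes.

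If 8 points is the effect over all six, the planned test has 89-96% power and only the text is wrong. If 8 points is the effect on the flawed three, a test of H1 has 74-81%, short of 80% over most of the stated ICC range, or about 81-88% with an assumed 20% vignette share. In that same case, with no effect on accurate vignettes, the pooled model actually planned has about 35-47%. This dilution is the larger risk, and it is an assumption at the unfavourable end of a range rather than a forecast.

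All figures rest on the vignette-level reading of the SD and on the same SD and ICC in the flawed subset.

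**What to change.** Before outcome data are seen:

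1. Name the vignette set for the primary test: the three flawed, as H1 is worded, or all six, as Section 4.2 is written.
2. State that the 8 points and the SD of 16.2 refer to that set, and say at which level the SD is defined.
3. Make H1, Section 4.2 and Section 2.3 refer to the same set.
4. Replace the 4 with the number of vignettes expected under Section 2.4 for that set, or state that it is an allowance for non-completion.
5. Restate power for the planned 50 participants over the ICC range, without enrolling more.

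The cost is text only. If the flawed-only test is chosen with 8 points, the stated power may be less favourable than the current claim, and it should be reported as it is.

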2.4 Clinical Vignettes & LLM Recommendations

Participants will evaluate six clinical vignettes specifically designed to measure automation bias. These vignettes will:

- Be based on modified real cases.
- Represent a range of diagnostic complexity across common medical specialties.
- Avoid overly simplistic or extremely rare conditions.
- Follow a standardized format, including:
 - Chief complaint and history of present illness.
 - Relevant past medical, social, and family history.
 - Physical examination findings.
 - Initial laboratory results.
- Include three clinical vignettes whose LLM recommendations contain deliberately introduced clinical reasoning errors and three with accurate recommendations, presented in randomized order. A panel of three licensed physicians will design these errors to be subtle yet clinically significant and detectable by trained clinicians.

- For every vignette, the LLM's recommendations will be pre-generated and fixed. This ensures all participants see identical recommendations for each vignette, the same error in flawed cases and the same correct reasoning in accurate cases, eliminating variance from real-time model variability.

Vignette Selection and Validation:

- A pool of 10 potential vignettes will be created and reviewed by an independent panel of three experienced medical doctors for:
 - Clinical accuracy and realism.
 - Appropriateness of difficulty level.
 - Clarity and completeness of information.
 - In flawed vignettes: subtlety and clinical significance of the introduced errors (errors should be detectable by competent physicians but not immediately obvious).
- Six vignettes will be selected based on the panel's ratings and feedback, aiming for a balanced representation of medical specialties and diagnostic challenges.
- For intervention arm participants, LLM output will be pre-generated and standardized for each vignette to ensure consistency in the presentation of correct or flawed information.

Vignette Completion:

- Each participant will complete all six vignettes in a single, proctored, approximately 75-minute session.
- The order of vignettes will be randomized for each participant to control for order effects and prevent pattern recognition.

2.5 Data Collection

2.5.1 Session Protocol

- Participants will complete the study under proctored conditions (in person or via secure video conferencing).
- Participants will complete a brief baseline questionnaire collecting demographic information (gender, specialty, years of experience), technology proficiency, and prior LLM experience.
- Participants will receive instructions specific to their assigned group (intervention or control).
- Participants will evaluate clinical vignettes one at a time.
- For each vignette, participants will provide:
 1. Their top three differential diagnoses.
 2. Supporting and opposing factors for each differential diagnosis (clinical findings, test results, etc.).
 3. Their most likely final diagnosis.
 4. Recommended next steps in the diagnostic workup (e.g., further tests, consultations).
- Participants will record all responses using a standardized electronic form.
- Time spent per vignette will be automatically tracked.
- For each vignette, a binary indicator will record whether the participant accessed the LLM recommendations (1 = viewed; 0 = not viewed).

3 Outcome Measures

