Participants will be randomly assigned to control or treatment arms. Both groups will evaluate six clinical vignettes accompanied by LLM-generated recommendations, three of which contain deliberately introduced errors that are subtle yet clinically significant. LLM consultation will be discretionary, physicians will choose whether to view ChatGPT recommendations for each case.

The control arm will receive these recommendations without additional context. The treatment arm will receive a behavioral nudge intervention leveraging complementary cognitive mechanisms: (1) an anchoring cue displaying ChatGPT's average diagnostic reasoning accuracy on standard medical datasets before evaluation begins, establishing realistic performance expectations, and (2) a selective attention cue enabling deeper System 2 engagement through color-coded confidence signals when participants view ChatGPT recommendations. These confidence signals are generated through ensemble assessment: three independent state-of-the-art LLMs (Claude Sonnet 4.5, Gemini 2.5 Pro Thinking, and GPT-5.1) each provide confidence ratings for the recommendation, and the mean confidence determines the signal color. Multi-model aggregation mitigates the systematic overconfidence of single-model confidence reports, yielding more robust uncertainty estimates. Red signals indicate mean confidence below ChatGPT's baseline accuracy on medical benchmarks, prompting heightened critical scrutiny. Orange signals indicate above-baseline but less than 100% confidence, deliberately using orange rather than yellow to prevent complacency. Green signals indicate high ensemble confidence ($= 100\%$), though standard AI safety warnings apply (e.g., "AI may make mistakes. Always double-check.").

Clinical vignettes will be randomly sequenced to prevent pattern detection. By comparing diagnostic accuracy scores between arms, we will quantify the degree of automation bias in the control group and assess whether the behavioral nudge intervention reduces uncritical acceptance of erroneous AI-generated recommendations in the treatment group. This design enables

us to isolate both the magnitude of automation bias and the causal impact of transparency-based interventions on physician decision-making.

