4.6 Exploratory Analyses

- **Differential Impact of Confidence Signals:** We will compare diagnostic scores for vignettes receiving Red Signal (flawed) versus Orange Signal versus Green Signal by group.

- **Chronometric Analysis of System 2 Engagement:** Using timestamps, we will compare time spent on Red Signal versus Orange Signal vignettes within the Treatment group. Longer durations on Red Signal vignettes would indicate deeper System 2 processing.
- **Physician-Case Specialty Match:** Exploratory analysis will test whether automation bias is lower when a vignette matches the physician's specialty, independent of AI accuracy or signal type.

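### The exploratory System 2 timing analysis needs the moment of panel opening, which the specified data do not record, so time before and after the colour was seen cannot be told apart

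*Combined protocol and SAP*

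**What the plan says.** Section 2.5.1 (Session Protocol) lists two process measures for each vignette. One is a time: "Time spent per vignette will be automatically tracked". The other is access: "a binary indicator will record whether the participant accessed the LLM recommendations (1 = viewed; 0 = not viewed". No start or stop event is given for the time, and no time is attached to the access indicator.

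Section 2.1 (Study Design) fixes when the colour is first seen in the intervention arm: "Upon expanding the LLM recommendation panel for any vignette, participants will be presented with two synchronized cognitive cues". The colour signal is the second of those cues. The Introduction makes opening optional: "LLM consultation will be discretionary, physicians will choose whether to view ChatGPT recommendations for each case".

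Section 4.6 (Exploratory Analyses) then plans the timing analysis: "Using timestamps, we will compare time spent on Red Signal versus Orange Signal vignettes within the Treatment group". It also gives the interpretation in advance: "Longer durations on Red Signal vignettes would indicate deeper System 2 processing".

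The access indicator reappears only in section 4.1, as a descriptive consultation rate. Section 4.6 does not use it to restrict or divide the timing data.

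**The concern.** A signal that has not been seen cannot change how long a physician works. For an opened vignette, the recorded time contains a part before the colour was on screen (reading the case and perhaps listing differentials) and a part after it. Only the second part can show a response to that vignette's colour. Section 2.5.1 asks for three differentials, supporting and opposing factors, a final diagnosis and next steps, and nothing says at what stage of this work the panel is opened. The part before opening could be short or long.

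Two things are at stake. First, if Red vignettes take longer, the specified data cannot show whether the extra time fell before or after the signal. Second, the yes/no indicator gives the same value to a physician who opens the panel at once and to one who opens it as a final check after entering a diagnosis. In a trial of automation bias that is an informative distinction. It cannot be recovered after the sessions if it was not logged.

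The problem remains when every panel is opened. Dropping never-opened vignettes removes cases in which no colour was seen, but it does not divide the time within an opened one.

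**Working it through.** **Figures in the plan.** The plan gives no variance, effect size or power for timing. The power statement in section 2.3 concerns the diagnostic reasoning score and does not bear on this point. The one usable timing figure is in section 2.4: six vignettes in about 75 minutes, so 75/6 = 12.5 minutes each on average.

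**Set-up.** For an opened vignette, write total time T = A + B, with A the time before first opening and B the time after. Let b be the Red-minus-Orange difference in mean A, and D the same difference in mean B. The observed difference in mean T is b + D.

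**Bias.** The colour is unseen during A, so that vignette's colour contributes nothing to b. If Red and Orange cases are alike, b = 0 and the raw difference in minutes equals D, so pre-opening time does not bias it. If the cases differ in length or difficulty, b need not be zero and can have either sign. Total time shows b + D and cannot separate the two terms. Section 4.6 itself associates Red with the flawed vignettes, so the two sets are not interchangeable by design.

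**Sensitivity, taking b = 0.** Let k = Var(A)/Var(B), and let r be the correlation of A and B.

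- Standardised effect on post-opening time: D / SD(B).
- Standardised effect on total time: D / SD(T), where Var(T) = Var(B) × (1 + k + 2r√k).
- Ratio of the second to the first: 1 / √(1 + k + 2r√k).

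The values of k and r below are assumptions; the documents supply neither.

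| k | r = -0.5 | r = 0 | r = 0.5 | r at which the ratio is 1 |
|---|---|---|---|---|
| 0.5 | 1/√0.793 = 1.12 | 1/√1.5 = 0.82 | 1/√2.207 = 0.67 | -0.35 |
| 1 | 1/√1 = 1.00 | 1/√2 = 0.71 | 1/√3 = 0.58 | -0.50 |
| 2 | 1/√1.586 = 0.79 | 1/√3 = 0.58 | 1/√4.414 = 0.48 | -0.71 |

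The last column is r = -√k/2. Below it the ratio exceeds 1: at k = 1 and r = -0.7 it is 1/√0.6 = 1.29, and total time is then the more sensitive measure.

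**Which sign of r is plausible?** Both are. A physician who is slow throughout makes A and B rise together. A physician who fills in the form before opening moves work from B to A, which makes them move in opposite directions. The plan does not settle which dominates.

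**The case against.** The strongest reply is that section 4.6 speaks of timestamps, in the plural, and section 2.5.1 nowhere says that the time is a total. The platform may already log panel opening. That stands as far as it goes: the exact criticism is that the stamped events are not specified. It does not remove the point, because section 4.6 names its outcome as time on vignettes and section 2.5.1 lists no opening time. If opening is already logged, the fix is a clarification.

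A reader might infer more than the documents support, in two ways.

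- *That pre-opening time invalidates the System 2 inference by itself.* It does not. With like cases, expected pre-opening time is the same for both colours, and the difference in minutes is unbiased, though the variance may change. Systematic error from this source needs case differences.
- *That the signal effect is diluted by a known amount.* Figures such as 0.82, 0.71 and 0.58 hold only if the two segments are independent. The mechanism that makes opening time matter, work shifted from after opening to before it, pushes the correlation negative, and the loss can then vanish or reverse.

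It is also fair to object that time from opening to submission is no clean measure. A physician who opens at once has all the reading and form-filling counted as post-signal time; one who opens late has almost none. That stands, and it is a reason not to make post-opening time the sole main measure.

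Finally, this is one bullet among the exploratory analyses. None of H1 to H3 is stated in terms of time.

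**Conclusion.** The point holds as a gap in the data specification for an exploratory analysis. As written, the plan cannot separate time before the colour was seen from time after it, so a longer total on Red vignettes does not by itself show a response to the signal.

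The size of any loss is unknown. Under assumed variance ratios of 0.5 to 2 and correlations of -0.5 to 0.5, the standardised effect on total time ranges from 0.48 to 1.12 of the post-opening effect. Neither a fixed dilution nor a bias in like cases can be claimed.

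The case for acting does not depend on those figures. The opening time is cheap to log and cannot be recovered later, and it gives a check on case differences that total time cannot give. The primary outcome, the secondary outcome and the stated power are unaffected. This is a worthwhile low-cost improvement and not a defect in the main analysis.

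**What to change.** In section 2.5.1, define the start and stop events for vignette time. Add two logged items per vignette: the time of first panel opening, and whether the final-diagnosis field was already filled at that moment.

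In section 4.6, for opened vignettes:

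- Report pre-opening and post-opening time alongside total time.
- Use the Red-Orange difference in pre-opening time as a check for case differences, since that vignette's colour cannot cause it.
- Attribute longer Red time to the signal only if the difference lies in post-opening time. This is necessary but not sufficient, because the content read after opening also differs between cases.
- Take the timing of opening into account when interpreting post-opening time.

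Report consultation separately for panels opened before and after a diagnosis was entered, next to the overall rate in section 4.1.

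The cost is one timestamp and one field-state indicator on a custom platform that already tracks time, plus a few sentences in the plan, all before the first session. The downsides are that the split exists only for opened panels and that post-opening time depends on when the physician chose to open. Total time should therefore be kept.
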